### ***Statistical criteria***

All statistical calculations will be made using two groups of statistical criteria:

- parametric - to obtain effective estimates for random parameters in case the relevant conditions of method/model applicability are not violated (e.g. sphericity, normality, risk proportionality, etc.)
- nonparametric – in all other cases.

 Adaptive Increase in Sample Size when Interim Results are Promising: A Practical Guide with Examples. Cyrus R. Mehta, Stuart J. Pocock. Statistics in Medicine 2000; 00:1–6.

 Taking into account the elimination - up to 680.

***Parametric criteria***

The application of parametric criteria will be accompanied by a check of models for applicability (e.g. Kolmogorov-Smirnov test, Shapiro-Wilk test).

The following parameters and approaches are to be used:

1. To evaluate the differences in continuous variables obtained in one group at two different visits – Student’s test for matched samples.
2. To evaluate the time changes of the compared indicators - variance (ANOVA) or covariance (ANCOVA) analysis in modification with repeated measures (Repeated Measures).
3. In case of multiple comparisons of the groups various corrections for multiplicity will be used, e.g. Dunnett, Tukey, Scheffe, Holm adapted test, etc.
4. Generalized Linear Models and/or Mixed Linear Models will be used in case of abnormal data distribution.
5. Selection of the type of distribution, specification of factor and covariance structures of the model will be made using fit-statistics such as AIC (Akaike information criterion).

The following SAS software programs are supposed to be applied to the above listed tests and techniques:

- UNIVARIATE – normality verification of the distributions under comparison
- CORR, MEANS – calculation of descriptive statistics
- TTEST – Student’s test with all modifications
- GLM – generalized linear models for analysis of time changes (ANOVA, ANCOVA)
- GENMOD – generalized linear models
- MIXED – mixed linear models.

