### **Endpoints**

#### ***Primary endpoint***

1. Change in the mean FSS score after 4 weeks of treatment.

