#### ***Secondary endpoints***

1. Change in the 6-minute walk distance after 4 weeks of treatment.
2. Change in the severity of anxiety and depression as estimated by the HADS subscales after 4 weeks of treatment.
3. Change in the mean FSS score in the course of the 4-week follow-up.
4. Change in the 6-minute walk distance in the course of the 4-week follow-up.
5. Change in the severity of anxiety and depression as estimated by the HADS subscales in the course of the 4-week follow-up.
6. Changes in vital signs after 4 weeks of treatment and in the course of the 4-week follow-up.
7. Occurrence and nature of adverse events, their intensity (severity), causal relationship to the study drug, and outcome.

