## **Interim analysis**

A non-blind interim analysis will be carried out after 62 PP subjects complete the trial. Based on the results, the sample size may be increased up to 680 subjects (with the maximum number of randomized subjects being n=646).

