#### **Primary Criteria:**

$$\mathbf{H_0: M_1 - M_2 = 0}$$

$$\mathbf{H_a: M_1 - M_2 \neq 0}$$

---

 Mehta, C.R. and Pocock, S.J. (2011), Adaptive increase in sample size when interim results are promising: A practical guide with examples. *Statist. Med.*, 30: 3267-3284. <https://doi.org/10.1002/sim.4102>.

where  $M_1$  and  $M_2$  are values of change in the mean score of the questionnaire in the Placebo and Prospekta groups;

The following SAS code was used to determine the required sample size:

executable SAS code (also defines critical statistics for the corresponding analyses)

```
Proc seqdesign errspend
Design nstages = 2
Info = cum (0.25,1)
Method (alpha) = UNI (rho = 0.5 tau = 0)
Method (beta) = UNI (rho = 0 tau = 0)
Stop = reject
Alpha = 0.05
Beta = 0.2
Samplesize model = twosamplemeans (meandiff = 0.65 stddev = 1.81)
Run.
```

1.8 the full sample size is determined by the formula:

$$N = N_{PP} / (1 - K_B)$$

where  $N$  – terminal sample size;  $N_{PP}$  – sample size in c. 1.7 i.e. scheduled number of subjects completing the study per protocol;  $K_B$  – withdrawal rate.

2. Assumptions on expected clinical study effects:

It is assumed that there is **an inter-group difference between the changes in the mean score of the FSS 0.65** questionnaire in favor of the Prospekta (the adaptation process assumes a possible deterioration in the effect prediction size to 0.41).

**Population standard deviation of change:** assumed to be 1.81. Thus, for the first stage (before adaptation), the size of each of the groups of 122 clinical study subjects is required (PP sample). Considering the possible elimination of about 10% of the subjects in the study for various reasons, at least **272** subjects will be required to sign informed consent, of which 260 subjects of clinical trial will be randomized (**130** subjects of clinical trials to each group) (see item 1.8, the final complete elimination rate will be  $K_B = 0.1$ ).

---

 Minimum size for this study

 The change in the average FSS score was indicated during the study, for the calculation of which the sum of points on nine points is divided by 9 (the average score lies in the range [1; 7]).

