### ***Sample size adaptation***

It is planned to adapt the sample size during the study according to the following algorithm^8:

- 1) During the planned interim analysis (if the study was not completed due to the rejection of the null hypothesis based on the interim analysis boundary), the conditional power is calculated by the formula:

$$CPower = 1 - \Phi \left( \frac{z_{\alpha} * \sqrt{N_{min}} - z_1 * \sqrt{N_1}}{\sqrt{N_{min} - N_1}} - \frac{z_1 * \sqrt{N_{min} - N_1}}{\sqrt{N_1}} \right)$$

where  $Z_1$  – value of Z-statistic obtained from interim analysis on  $N_1$  of the first participants from  $N_{min}$  (minimum study sample size);

$Z_{\alpha} = 1.9603$  (the value of statistics for the final analysis, taking into account the presence of an interim analysis);

$\Phi(x)$  – probability value of event X for standard normal distribution ( $\sigma=1, \mu=0$ ).

- 2) Maximum allowable increase in sample size to no more than 612 is assumed.
- 3) Assumed minimum sample size  $N_{min} = 260$ .
- 4) Based on the above, one of the adaptation scenarios will be selected.
- 5) Optimistic scenario (conditional power  $CPower > 0.8$ , or equivalently  $Z_1 > 1.3545$ ): the sample size does not change ( $N_{final} = N_{min}$ ).
- 6) Mid-range scenario (conditional power  $0.397 < CPower < 0.8$ , or equivalently  $0.8744 < Z_1 < 1.3545$ ): the sample size changes according to the formula:

$$N_{final} = N_1 + \left( \frac{N_1}{z_1^2} \right) * \left( \frac{z_{\alpha} * \sqrt{N_{min}} - z_1 * \sqrt{N_1}}{\sqrt{N_{min} - N_1}} + z_{\beta} \right)^2$$

- 7) Pessimistic scenario (conditional power  $CPower < 0.3975$ , or equivalently  $Z_1 < 0.8744$ ): sample size does not change ( $N_{final} = N_{min}$ ).
- 8) The final statistical analysis is carried out with the critical values obtained during the assessment of the minimum sample size ( $Z_{\alpha} = 1.9603$ ).

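### No single test is fixed for the primary Week 4 FSS comparison, so the model behind the Z that sets the sample size and decides the final test is undefined

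*Combined protocol and SAP*

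**What the plan says.** - **Endpoint and hypotheses.** The primary endpoint is "Change in the mean FSS score after 4 weeks of treatment". Under Primary Criteria the hypotheses concern M1 - M2, where M1 and M2 "are values of change in the mean score of the questionnaire in the Placebo and Prospekta groups". FSS over the follow-up is a separate, secondary endpoint: "Change in the mean FSS score in the course of the 4-week follow-up".
- **Sizing.** The SAS planning code contains "Samplesize model = twosamplemeans (meandiff = 0.65 stddev = 1.81". This sizes the trial; it is not declared to be the analysis.
- **Methods.** Item 2 under Parametric criteria reads "To evaluate the time changes of the compared indicators - variance (ANOVA) or covariance (ANCOVA) analysis in modification with repeated measures (Repeated Measures". Item 1 there is a within-group paired test. Items 4 and 5 bring in generalized and mixed models for non-normal data and leave distribution, factor and covariance structure to fit statistics such as AIC. Statistical criteria sends the analysis to nonparametric methods when model conditions fail. The procedure lists add TTEST in all its variants and the Mann-Whitney test. None of these is tied to the primary endpoint.
- **Interim.** "A non-blind interim analysis will be carried out after 62 PP subjects complete the trial". Sample size adaptation defines Z1 as the "value of Z-statistic obtained from interim analysis on" the first N1 participants, without naming the test. Item 8 of that section says: "The final statistical analysis is carried out with the critical values obtained during the assessment of the minimum sample size", that is 1.9603.

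**The concern.** The trial has one number, Z, that does two jobs. At the interim it chooses between keeping the minimum sample size and enlarging the trial; at the end it is compared with 1.9603. A change-score t-test, an ANCOVA and a Mann-Whitney test on the same 62 subjects give different values of Z. The plan does not say which one counts, and its stated rules make the choice depend on the data. The interim is unblinded, so the statistic could be settled with arm-level results in view.

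What is at stake at the interim is mainly the sample size, since early stopping is improbable even at the planned effect. At the final look it is the credibility of the one confirmatory p-value.

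**Working it through.** **1. The plan's own figures reproduce.** Inputs from Evaluation of sample size: difference 0.65, SD of change 1.81, two-sided alpha 0.05, power 80%.

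- n per arm = 2 x (1.96 + 0.8416)^2 x 1.81^2 / 0.65^2 = 121.7, so 122.
- Power at 122 = Phi(0.65 / (1.81 x sqrt(2/122)) - 1.9603) = Phi(2.805 - 1.960) = 80.1%.
- A two-look O'Brien-Fleming boundary at information 0.25 and 1 gives |Z| of 3.92 and 1.9603. Expected Z1 at 31 per arm is 0.65 / (1.81 x sqrt(2/31)) = 1.41, so the chance of stopping early is about 0.6%.

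**2. How much hangs on Z1.** The conditional-power formula under Sample size adaptation, with N1 = 62 and N_min = 244:

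| Z1 | First term | Second term | Conditional power | N_final by the item 6 formula |
|---|---|---|---|---|
| 0.8744 | 1.759 | 1.498 | 0.397 | 610.6 |
| 1.3545 | 1.479 | 2.321 | 0.800 | 244.0 |

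These match the stated limits. (Item 3 gives N_min = 260; with that value the conditional powers are 0.423 and 0.824, and N_final at 0.8744 is 609.6.) Just below 0.8744 the size stays at N_min, and just above it rises to about 610, a step of about 367 subjects (610.6 - 244). The zone rule creates that step and it would exist with any statistic, but it makes small differences in Z1 matter.

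**3. How often candidate statistics disagree at 31 per arm.** The documents give no baseline SD and no baseline-to-Week 4 correlation (rho), so two families of assumptions were simulated.

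- *Family A:* FSS bounded 1-7, entry at mean score 4 or more, Week 4 SD about twice the baseline SD, SD of change 1.74-1.83, observed effect 0 or 0.32-0.67.
- *Family B:* normal data, equal variances at both visits, rho 0.3-0.7, SD of change 1.81, effect 0 or 0.65.

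| Different adaptation zones | A, null | A, effect | B, null | B, effect 0.65 |
|---|---|---|---|---|
| t-test vs ANCOVA | 3.6-8.4% | 6.1-14.7% | 12.4-18.0% | 22.0-32.5% |
| t-test, ANCOVA and Mann-Whitney not all in one zone | 7.5-11.8% | 12.2-20.3% | not tabulated | not tabulated |

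**4. Type I error at 122 per arm, no effect.** A mechanical Shapiro-Wilk switch gives 4.7-5.2% (family A). Reporting the best of t-test, ANCOVA and Mann-Whitney would give 5.9-6.7% (A) or 7.7-8.7% (B). Generalized, mixed and AIC-selected models were not simulated.

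**5. Raw t is not Z.** An ANCOVA on 62 subjects has 59 df. There t = 0.8744 is Z = 0.868, which is on the other side of the limit, and t = 1.3545 is Z = 1.338. At the final look (241 df) t = 1.9603 has p = 0.0511. The shifts are small, but the conversion has to be stated.

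**6. Effect of fixing ANCOVA.** Its variance relative to the change score is 0.94-1.00 in family A, so power at 122 is 80.2-82.5%. In family B the ratio is (1 + rho)/2 = 0.65, 0.75, 0.85 for rho = 0.3, 0.5, 0.7, so the residual SD is 1.46, 1.57, 1.67 and power is 93.6%, 90.0%, 86.0%.

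**The case against.** - **The planning code implies a t-test.** It does let a reader infer one. But it is sizing code, and the later sections make the method depend on the data, so it does not settle the analysis.
- **The harm is limited.** This stands in part. The plan describes a switch, and a mechanical switch holds type I error near 5%. A reader might infer error inflated to 6-9%; that needs free choice of the best result, which the plan does not describe, so it is only an upper bound for those three tests. Disagreement between valid statistics is noise rather than bias. The objection does not remove the need to say which Z drives an unblinded decision.
- **Direction.** A reader might infer that the sign of Z is also undefined. It can be derived: M1 - M2 is Placebo minus Prospekta, the assumed 0.65 favours Prospekta, and with change taken as Week 4 minus baseline a positive value means a larger FSS fall on Prospekta.
- **Week 8 data.** Because the 62 interim subjects have completed the trial, a reader might infer that a repeated-measures model could average Weeks 4 and 8. The endpoints rule this out: the primary is at 4 weeks and follow-up FSS is secondary. A group-by-visit F test over three visits cannot supply a signed Z either.
- **AIC.** Items 4 and 5 can be read together, so that AIC only shapes the models used for non-normal data. Even so, the structure of a possible primary model is left to the data.
- **Status of the text.** It calls itself a protocol summary; the point concerns what is written there.

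**Conclusion.** The gap is real and should be closed before the unblinded interim. No section names the test for the Week 4 between-group comparison, and the same unnamed statistic feeds conditional power, the zones and the 1.9603 test. That no test is assigned is certain from the text.

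The size is not certain. t-test and ANCOVA land in different zones in about 4-8% of null trials and 6-15% with an effect under family A, and in 22-33% at the planned effect under family B. The ranges differ because they rest on assumed variances and correlations that the documents do not give, so neither should be read as a precise estimate. The finding concerns the definition of the primary statistic. It does not show that the planned procedure inflates type I error, nor that the sample size or the final critical value is wrong.

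**What to change.** State one primary analysis for both looks, to be used whatever the normality tests or AIC show:

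1. ANCOVA of the change in mean FSS from Visit 1 to Visit 2, with treatment as factor and Visit 1 mean FSS as covariate.
2. One named analysis set. The Samples section plans both ITT and PP analyses without calling either primary, while the interim is counted in PP subjects. If the Full Analysis Set is named, say how a missing Week 4 score is handled.
3. Z = Phi^-1(1 - p/2) from the two-sided p-value of the treatment contrast, signed positive when FSS falls more on Prospekta, in line with M1 - M2. This Z is Z1 in Sample size adaptation and is compared with 1.9603 at the final look.
4. All other listed methods (change-score t-test, Mann-Whitney, repeated-measures, generalized, mixed and AIC-selected models) labelled as sensitivity analyses that do not feed the adaptation.

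The cost is SAP wording, with data already collected. 122 per arm and 1.9603 are unchanged; power at 122 is about 80-94% depending on the assumed correlation, against 80.1% unadjusted. A change-score t-test fixed in advance would also define Z and matches the sizing model. ANCOVA is preferred because baseline FSS is already recorded and no loss of power is expected.

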***Non-parametric criteria***

Below are potential types of comparisons with relevant criteria:

1. To evaluate time changes in the parameters compared – Friedman test, nonparametric analogue of repeated measures analysis of variance.
2. For frequency analysis of contingency tables  $2 \times 2$  –  $\chi^2$  (if the frequency under comparison  $> 5$ ) or exact Fisher’s test (if one of the frequencies under comparison  $< 5$ ).
3. Cochran-Mantel-Haenszel test (modified  $\chi^2$  test for multiple comparisons) – to perform frequency analysis based on independent strata.
4. For frequency analysis of data on presence/absence of an event or outcome during repeated measurements (contingency tables with dependent strata) – survival analysis.

To perform the above-mentioned nonparametric statistical analysis the following SAS procedures are to be used:

- FREQ – Friedman test,  $\chi^2$  test and/or exact Fisher’s test; Cochran-Mantel-Haenszel test

- LIFETEST, PHREG – survival analysis
- NPAR1WAY - Mann-Whitney U-test

***Safety parameters***

Adverse events recorded during the study will be grouped into frequency tables by severity, seriousness and relationship with the study drug.

***Data presentation***

Descriptive statistics will be provided for each study continuous / interval variable. Numerical data will be presented by mean, standard deviation, as well as maximum and minimum values, as well as 1, 2 and 3 quartiles (if necessary, other measures of central tendency and spread can be additionally given). The categorical variables will be presented as frequency tables by visits.

Outliers will be analyzed individually. The data will be grouped by visits.
